4.7.1.4 Handling Plan for Missing Data

Missing visits, due to skipped visits or early dropout of study, will be imputed using the last observation carried forward (LOCF).

4.7.1.5 Sensitivity Analysis of the Primary Efficacy Endpoint

The sensitivity analysis of the primary efficacy endpoint will be performed using all available data in the same way as the primary analysis. The data collected after administration of the prohibited medications or discontinuation of study treatment will be included in the analysis. No data will be imputed for missing visits.

4.7.2 Secondary Efficacy Endpoints and Analyses

4.7.2.1 Secondary Efficacy Endpoints

The secondary efficacy endpoints are as follows:

- Percent change from baseline in SALT score at Weeks 12-20, 28-36, and Weeks 40-48.
- Proportion of participants who achieve ≥ 50% reduction in SALT from baseline at Weeks 12-36 and Weeks 40-48.
- Proportion of participants with absolute SALT score $\leq 10, 20, 30, 50$ at Weeks 12-36 and Weeks 40-48.

4.7.2.2 Secondary Efficacy Analyses

The continuous secondary efficacy endpoints will be summarized in the same way as the primary efficacy endpoint, including handling plan for prohibited medication use, treatment discontinuation and missing data (Section 4.7.1.3 and Section 4.7.1.4). Spaghetti plots of SALT score by participant over time will be presented. In addition, percent change from baseline in SALT score over time will be analyzed by baseline IFN gene signature levels (high versus low).

The binary secondary efficacy endpoints will be summarized descriptively using frequencies and percentages. A 2-sided 95% confidence interval will be calculated for the percentage. The participants will be considered non responder after administration of the prohibited medications that are considered to be effective for treatment of AA. The data collected after discontinuation of study treatment will be included in the analyses. Missing visits due to skipped visits will be imputed using the last observation carred forward (LOCF), and the participants will be considered non-responders after early dropout of study.

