6.3.1 Blinding

This is an open-label trial. Participants and investigators are aware that the IP is daxdilimab.

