8.1.1 Severity of Alopecia Tool (SALT)

To participate in this trial, a participant must have moderate-to-severe AA as assessed by a SALT score of \geq 50 and \leq 95 at screening and baseline (Day 1) as described in Section 5.1.

The SALT score is a well-validated metric and widely utilized tool for determining the degree of hair loss based on the percentage of scalp surface area involved on the top, back, and each side of the scalp for AA. The investigator will determine the percent scalp hair loss in a given quadrant, multiply this by the total scalp area delineated by that quadrant, and sum the resultant numbers for each quadrant to give the total percent scalp hair loss with a maximum score of 100.²¹ The SALT assessment tool is provided in Appendix 1.

8.1.2

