2.3 Sample Size

A total of up to 30 participants will receive daxdilimab in the trial. The sample size was determined by the need to evaluate potential efficacy, safety and tolerability, and PK/PD. No formal power calculation was performed.

The mean percent reduction from baseline in SALT score was 58% in 4 mg group at Week 36 in Eli Lilly's phase 2 AA trial (n=28) (King B, Ko J, Forman S, et al., 2021). The lower bound of the 95% confidence interval was about 42%. With 30 participants, if we observe a mean percent reduction from baseline in SALT score of 58% at Week 24, there is about 98% confidence that the mean percent reduction from baseline is at least 42%. The estimated confidence level that true mean percent reduction from baseline in SALT score is above a cutoff for an observed mean is provided in Table 2.

Table 2Confidence level that true mean percent reduction from baseline in SALT
score is above a cutoff for an observed mean

	Observed		Confidence that mean is	5
n	Mean % reduction	≥35%	≥42%	≥45%
30	50%	0.97	0.85	0.74
	55%	>0.99	0.95	0.90
	58%	>0.99	0.98	0.95

The proportion of patients achieving SALT ≤ 20 at Week 36 in 4 mg group was 33% and 35% in two Eli Lilly's phase 3 AA trials. The lower bound of the 95% confidence interval was about 27%. The estimated confidence level that true proportion of participants achieving SALT ≤ 20 is above 27% and other cutoffs for an observed response rate is provided in Table 3.

Table 3	Confidence level that true proportion of participants achieving SALT ≤ 20
	is above a cutoff for an observed response rate.

	Observed	Confidence that response rate is		
n	response rate	≥20%	≥25%	≥27%
30	9 (30%)	0.87	0.67	0.58
	11(36.7%)	0.97	0.89	0.84
	12(40%)	0.99	0.95	0.92
	13(43.3%)	0.99	0.98	0.96
	15(50%)	0.99	0.99	0.99

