4.10 Pharmacodynamics

Descriptive summaries will be presented by visit for the following:

- pDC levels (DC flow cytometry)
- whole blood transcriptomics (eg. IFN gene signature)

Descriptive statistics will be presented for PBMC assays as well as serum IFN-a and other serum/plasma biomarkers or factors that may be associated with the daxdilimab mechanism of action or AA disease pathways when applicable and if data allows.

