4.11 Immunogenicity

The ADA status will be summarized for the safety analysis set by the categories defined in Table 4. The ADA incidence rate may also be summarized, where the incidence is the proportion of the participants with ADA positive post-baseline only or boosted their preexisting ADA during the study period. The cutoff for the boosted ADA will be determined before the database lock for the primary analysis. If data allow, the ADA titer for the ADA positive participants will be summarized, and the impact of ADA on PK, efficacy and safety will be evaluated. Daxdilimab (HZN-7734) HZNP-DAZ-201

Statistical Analysis Plan

Version 1.0

Daxdilimab (HZN-7734) HZNP-DAZ-201

Statistical Analysis Plan

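### SAP 4.7.2.2 shows SALT response by baseline IFN signature only as high versus low, with no stated cut; fix one cut in advance and add a continuous analysis

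*SAP*

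**What the plan says.** Among the secondary efficacy analyses, SAP 4.7.2.2 states that "percent change from baseline in SALT score over time will be analyzed by baseline IFN gene signature levels (high versus low"). The only other visible reference to the signature is in SAP 4.10, which lists "whole blood transcriptomics (eg. IFN gene signature") among the pharmacodynamic measures to be summarised by visit. Neither place gives a gene set, a scoring rule, a threshold, the person who sets it, or a date.

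Other text that bears on the point:

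- **Size.** SAP 2.3: "A total of up to 30 participants will receive daxdilimab in the trial". There is one arm (Protocol 6.3).
- **Blinding.** Protocol 6.3.1: "This is an open-label trial. Participants and investigators are aware that the IP is daxdilimab". SALT is scored at site: "The investigator will determine the percent scalp hair loss in a given quadrant" (Protocol 8.1.1), at every visit in the Schedule of Assessments.
- **Looks at the data.** SAP 3.1 and 3.2 plan a primary analysis after Week 24 and a final analysis. Nothing says that one cut serves both.
- **Another cut-off in the same SAP.** SAP 4.11: "The cutoff for the boosted ADA will be determined before the database lock for the primary analysis". SAP 4.7.1.3 likewise sets a deadline for the list of prohibited medications considered effective for alopecia areata.
- **Type of output.** SAP 4.1 plans descriptive statistics. No test, alpha or decision rule is attached to the signature split.
- **Deferred detail.** The SAP sends data presentation, visit windows and date imputation to the SPP. It does not say that the signature cut is there.

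**The concern.** Two separate issues arise.

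The first is loss of information. If the signature is available as a score, splitting about 30 people into two groups discards the ordering within each group. A real gradient then becomes harder to see.

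The second is the open cut. Where the threshold is free and outcomes are visible, several splits can be tried and the most striking one shown. No blind stands in the way here, and no deadline is set. This matters even for a purely descriptive table, because the displayed gap between high and low grows with the freedom to choose, whether or not a p-value is printed.

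What is at stake is how the signature result is read. Protocol 2.1.2 rests the rationale for the drug on diseases partly driven by high type I interferon, so readers will give weight to a high/low contrast. The primary endpoint and its confidence interval are not affected.

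**Working it through.** **Step 1: the SD, from the plan's own table.** SAP 2.3 takes from the cited phase 2 trial that "The mean percent reduction from baseline in SALT score was 58% in 4 mg group at Week 36", with n=28 and a lower 95% bound of about 42%.

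- SD = (58 − 42)/1.96 × √28 = 43.2 (41.3 with a t quantile).
- With n=30, SE = 43.2/√30 = 7.89.
- Confidence that the mean is at least 42% when 58% is observed = Φ(16/7.89) = 0.979. The plan states 0.98.

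All nine cells of SAP Table 2 agree within 0.01, so an SD of 42 to 43 percentage points of percent change fits the plan. The documents give no figure for the signature split itself.

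**Step 2: what a free cut does when nothing is there.** Inputs: n=30; SALT percent change normal with SD 42, unrelated to the signature; a two-sample t-test at two-sided 0.05, used only as a yardstick. Each simulated trial is ordered by signature, every allowed cut is tried, and the most extreme result is kept (40,000 trials).

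| Cuts allowed | p<0.05, either direction | p<0.05, IFN-high better | Median largest gap, either direction (percentage points) |
|---|---|---|---|
| Fixed median, 15 v 15 | 5% | 2.4% | 10 |
| Median or tertiles | 11.5% | 6% | 18 |
| Any, at least 10 per group | 17% | 9% | 21 |
| Any, at least 8 per group | 21.5% | 11% | 23 |
| Any, at least 5 per group | 29% | 15% | 28 |

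The rates barely depend on the SD: at 43.2 the first column is 5%, 12%, 17%, 22% and 29%. The gap does scale with it. If only gaps in favour of IFN-high count, the best cut with at least 10 per group has a median gap of about 11 points, against 0 for a fixed median cut.

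**Step 3: what the split loses when a relation exists.** Assumed: bivariate normal signature score and SALT change, n=30, two-sided 0.05, 20,000 trials.

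| True correlation (assumed) | Regression slope | Spearman | Median split |
|---|---|---|---|
| 0.4 | 60% | 55% | 41% |
| 0.5 | 82% | 77% | 61% |

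**Step 4: precision of a pre-specified split.** With 15 v 15 and SD 42, the SE of the difference is 42 × √(2/15) = 15.3. The 95% half-width is 2.048 × 15.3 = about 31 percentage points. A fixed cut removes the selection but remains imprecise, which is a further reason to show the score as well.

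**The case against.** The strongest reply is that the rates in Step 2 belong to a test the SAP does not plan. The output is descriptive, carries no alpha or decision rule, and sits apart from the primary endpoint. That is correct, and the rates should be read only as a measure of how far a free cut can mislead. The widening gap in the last column does not depend on a test.

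Several other objections also stand:

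- **The cut may already exist.** High and low may be an established classification for the assay, or may be set in the SPP. In that case Step 2 does not apply. The visible SAP does not say so, and one sentence would settle it.
- **The score is an inference.** The documents name transcriptomics and a signature, not a continuous score, so the continuous analysis is conditional on one existing.
- **The widest search is the extreme case.** A choice among median and tertile cuts gives 11-12%, and about 6% in the IFN-high direction.
- **Some individual data will be shown.** SAP 4.7.2.2 already plans participant-level SALT plots, though it does not say that these are related to the signature.

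A reader might infer that this is the sponsor's only biomarker analysis of response, or that it would decide enrichment of a later trial. The documents support neither. Exploratory content is redacted, and no visible text mentions enrichment. A reader might also infer that the cut will be picked after looking at SALT. The open-label design makes that possible, but nothing says who sees SALT linked to signature data.

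**Conclusion.** The point holds as an inexpensive improvement to a descriptive secondary display. It is not a threat to the trial's main result. As visible, the SAP plans a two-group split of about 30 people with no cut and no deadline, although it sets deadlines for two other choices of the same kind.

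If the cut were chosen with SALT in view, the chance of a nominally significant but false association would rise from about 5% to 11-12% for conventional cuts, and up to 29% for an unrestricted search with at least 5 per group. In the IFN-high direction the rise is from about 2.5% to 6% and 15%. The typical largest gap would go from about 10 to about 20 percentage points of percent change when each group has at least 10. At a correlation of 0.5, a continuous analysis would detect the relation in 77-82% of trials, against about 60% for the median split.

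These figures assume normal data, 30 evaluable participants, an SD near 42 (implied by SAP Table 2), a signature available as a score, and the stated correlations. The result should not be called predictive: with one arm, neither a split nor a slope can separate prediction of drug benefit from prognosis.

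**What to change.** Amend SAP 4.7.2.2 in two places.

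1. **Add a continuous analysis, if the signature is available as a score.** Relate Week 24 percent change in SALT to the baseline score by Spearman correlation or a regression slope with a 95% confidence interval, and show a scatter plot. Describe the result as association with response.
2. **Keep the high/low display with one stated cut.** Use the assay's pre-existing cut-off if there is one, otherwise the median of the baseline values. Document it before signature data are linked to SALT, and use it unchanged in the primary and final analyses. Label any other cut post hoc. A deadline of database lock, as used for boosted ADA, would not be enough here, because SALT is visible before lock.

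If the SPP already defines the cut, a cross-reference with its date meets the second item.

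The cost is a few lines of SAP text and one extra table or plot from samples already scheduled on Day 1. The sponsor gives up the freedom to choose a later cut as the planned one, but can still show such a cut under a post hoc label.

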4.7.2.3 Sensitivity Analysis of the Secondary Efficacy Analyses

The sensitivity analysis for the continuous endpoints will be performed in the same way as the sensitivity analysis for the primary efficacy endpoint (Section 4.7.1.2).

The sensitivity analysis will be performed for the binary efficacy endpoints using all available data with the same method as the secondary efficacy analyses. Data collected after administration of prohibited medications or after discontinuation of study treatment will be

Daxdilimab (HZN-7734) HZNP-DAZ-201 Statistical Analysis Plan

included in the analysis. Missing visits due to skipped visits will be imputed using last observation carried forward (LOCF). Participants after early dropout of study will be considered as non-responders.

4.8 Safety Analyses

4.8.1 Adverse Events

In general, if an adverse event (AE) onset is on or after the first dose of IP, the AE will be considered as a treatment-emergent adverse event (TEAE). Otherwise, the AE will be considered as a non-TEAE.

AEs will be coded using the most recent version of MedDRA. All TEAEs will be summarized overall and by MedDRA system organ class (SOC) and preferred term (PT), by severity and by relationship to daxdilimab. Specific AEs will be counted once for each participant for calculating rates, but all events will be presented in participant listings. In addition, if the same AE occurs multiple times within a particular participant, the highest severity and level of causality will be reported.

An overall summary table will be showing the number and percentage of participants with at least one event in any of the following categories:

- TEAE
- Treatment-emergent serious adverse event (TESAE)
- TEAE resulting in death
- Grade 3 or higher TEAE

- TEAE leading to discontinuation of daxdilimab
- Serious and/or grade 3 or higher TEAE
- Daxdilimab related TEAE
- Daxdilimab related TESAE

The following AE summaries will also be provided by SOC and PT:

- TEAEs resulting in death
- Grade 3 or higher TEAEs
- TEAE leading to discontinuation of daxdilimab
- Daxdilimab related TEAE
- TESAEs
- Daxdilimab related TESAE
- Treatment-emergent adverse events of special interest (AESI, refer to protocol for detailed definition of AESI)

TESAEs will be summarized by serious adverse event (SAE) criteria as well. In addition, a summary of TEAEs sorted by frequency will be presented by PT. Listings will be provided for all TEAEs and non-treatment emergent AEs.

4.8.2 Clinical Laboratory Evaluations

The following summary will be provided for hematology and chemistry.

- Observed values and changes from the baseline by visit
- Worst toxicity grade
- At least 2-grade shift from baseline to worst toxicity
- Shift from the baseline relative to the normal range

In addition, the number and percentage of participants with the following liver-related abnormalities will be summarized if meet the following criteria at any post-baseline visit.

- AST or ALT: (a) \geq 3 × ULN; (b) \geq 5 × ULN; (c) \geq 8 × ULN
- Total bilirubin: $\geq 2 \times ULN$
- ALT or AST \geq 3 x ULN and total Bilirubin \geq 2 × ULN
- ALT or AST \geq 5 × ULN for more than 2 weeks

The following summary will be provided for urinalysis.

- Observed values and changes from the baseline
- Shift from the baseline relative to the normal range

Listings will be provided for all clinical laboratory evaluations.

4.8.3 Vital Signs

The observed values, along with the changes from baseline, will be summarized for systolic blood pressure, diastolic blood pressure, body temperature, heart rate, and respiratory rate. In

addition, a summary of participants with clinically significant vital signs values (meeting any of following criteria) will also be provided.

- Systolic blood pressure: < 90 mmHg, > 160 mmHg
- Diastolic blood pressure: < 60 mmHg, > 100 mmHg
- Heart rate: < 50 beats/min, > 100 beats/min
- Respiratory rate: < 12 breaths/min, > 23 breaths/min
- Temperature: < 36°C, >38°C

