5.2 Exclusion Criteria

Participants will be ineligible for trial participation if they meet any of the following criteria at the Screening and/or Day 1 visits, as applicable:

General Exclusion Criteria

- 1. Individuals involved in the conduct of the trial, their employees, or immediate family members of such individuals.
- 2. Any clinically significant medical condition or physical/laboratory/ECG/vital signs abnormality that would, in the opinion of the investigator, put the participant at undue risk or interfere with the evaluation of the IP or interpretation of trial results.
- 3. History of allergy, hypersensitivity reaction, or anaphylaxis to any component of the IP or to a previous mAb or Ig therapy.
- 4. Participant has had excessive sun exposure, is planning a trip to a sunny climate, or has used tanning booths within 4 weeks prior to Day 1 or is not willing to minimize natural and artificial sunlight exposure during the trial. Use of sunscreen products and protective apparel are recommended when sun exposure cannot be avoided.
- 5. Spontaneous or induced abortion or still or live birth ≤ 4 weeks prior to Screening.
- 6. Breastfeeding or pregnant women or women who intend to become pregnant anytime from signing the ICF through 6 months after receiving the last dose of IP or until the end of the trial, whichever is longer.
- 7. History of drug or alcohol abuse that, in the opinion of the investigator, might affect participant safety or compliance with visits, or interfere with other trial assessments.
- 8. Major surgery within 8 weeks prior to Screening or elective surgery planned during the trial.
- 9. Known history of a primary immunodeficiency or an underlying condition such as known human immunodeficiency virus (HIV) infection, a positive result for HIV infection, splenectomy, or any underlying condition that in the opinion of the investigator significantly predisposes the participant to infection.
- 10. At Screening, any of the following (tests may be repeated once within the same Screening period to confirm results prior to Day 1):
 - Aspartate aminotransferase (AST) $> 2.5 \times$ upper limit of normal (ULN)
 - Alanine aminotransferase (ALT) $> 2.5 \times$ ULN
 - Total bilirubin $> 1.5 \times$ ULN (unless due to Gilbert's syndrome)
 - Serum immunoglobulin G (IgG) $\leq 600 \text{ mg/dL}$ (or $\leq 6 \text{ g/L}$)
 - Neutrophil count $< 1000/\mu L$ (or $< 1.0 \times 10^9/L$)

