8.5 Safety and Other Assessments

8.5.1 Vital Signs

The following vital signs will be recorded at the visits specified in Table 1 with the participant in a seated or supine position, after having sat calmly for at least 5 minutes: systolic and diastolic blood pressure (mmHg), pulse (bpm), body temperature (°C), and respiratory rate (breaths/minute).

Weight (kg) and height (cm) will be collected to calculate the BMI, and will be recorded at the visits specified in Table 1. The height will only be recorded once at the screening visit and the same value will be used for BMI calculation at other visits.

If deemed appropriate by the investigator, clinically significant findings in the vital signs will exclude a participant from trial participation. Any abnormal finding related to vital signs that the investigator considers to be clinically significant must be recorded as an AE.

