4.8.5 Electrocardiogram Results

The observed values, along with the changes from baseline, will be summarized for ventricular heart rate, PR interval, QRS duration, QT interval, and the corrected QT interval (QTc). The number (%) of participants meeting the following criteria will be summarized:

- QTc > 450 msec
- QTc > 480 msec
- QTc > 500 msec
- QTc increases from baseline > 30 msec
- QTc increases from baseline > 60 msec

Corrected QT (QTc) intervals will be derived using Fridericia's correction (QTcF) and Bazett's correction (QTcB). In addition, the overall clinical evaluation of electrocardiogram results (normal, abnormal, not clinically significant abnormal, clinically significant abnormal) will also be summarized.

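### The vital-sign and absolute QTc threshold counts in SAP 4.8.3 and 4.8.5 do not separate values already outside the limit before dosing from new ones

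*SAP*

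**What the plan says.** **Vital signs (SAP 4.8.3).** The continuous summary uses baseline: "The observed values, along with the changes from baseline, will be summarized for systolic blood pressure, diastolic blood pressure" and the other signs. The threshold table does not: "a summary of participants with clinically significant vital signs values (meeting any of following criteria"). The limits that follow are absolute, for example diastolic pressure below 60 or above 100 mmHg.

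**ECG (SAP 4.8.5).** "The number (%) of participants meeting the following criteria will be summarized": three absolute rows (above 450, 480 and 500 msec) and two change rows, the first being "QTc increases from baseline > 30 msec" and the second the same at 60 msec.

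**Liver tests (SAP 4.8.2), for comparison.** The liver abnormalities "will be summarized if meet the following criteria at any post-baseline visit". The same section plans shifts from baseline against the normal range and shifts of at least two toxicity grades.

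**Entry and design (Protocol).** Exclusion 18 names a fever limit of 38.0°C on Day 1. Otherwise exclusions 2 and 19 leave vital-sign and ECG abnormalities to the investigator's opinion, without numbers. Section 6.3 states that everyone receives active drug. Section 8.5.1 leaves it to the investigator to decide whether a vital-sign finding is clinically significant, and such a finding must be recorded as an adverse event.

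**The concern.** A count of participants beyond a limit reads as something that happened on treatment. With no concurrent control, the only way to see whether it did is to look at the same participant before dosing. The SAP uses both of the usual devices elsewhere: the liver rows are post-baseline, and the other laboratory displays are shifts. The vital-sign list and the absolute QTc rows have neither. Taken literally, one pre-dose value could put a participant in the table.

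The title adds a second problem. It labels every crossing clinically significant, while the protocol gives that judgement to the investigator and ties it to adverse event recording. The table and the adverse event data then need not agree, and the difference would have to be explained.

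At stake is the reading of a descriptive safety table in up to 30 people, where one participant is 1/30 = 3.3 percentage points.

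**Working it through.** The plan states no figure for these counts, so there is none to reproduce. The check compares the displays and then sizes the effect on assumed inputs.

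**1. The displays side by side**

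| Display | Post-baseline only? | Baseline status used? | Numeric entry limit? |
|---|---|---|---|
| Vital-sign limits (4.8.3) | Not stated | No | Only fever on Day 1 |
| QTc >450, >480, >500 msec (4.8.5) | Not stated | No | None |
| QTc increase >30, >60 msec (4.8.5) | By construction | Yes | Not needed |
| Liver rows (4.8.2) | Yes | No | AST and ALT 2.5 × ULN; bilirubin 1.5 × ULN except in Gilbert's syndrome |

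Only the first two rows lack all the safeguards. The liver entry limits lie below the count thresholds (2.5 < 3 and 1.5 < 2).

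**2. Do the other outputs separate new from old?** A participant with QTc 452 msec before and after dosing has an increase of 0. That participant is absent from both increase rows but present in the row above 450. For vital signs the only baseline-referenced output is continuous change, which does not show which crossings are new.

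**3. How many could start outside a limit?** Let q be the share outside at baseline (assumed). The expected number is 30q, and the chance of at least one is 1 − (1 − q)^30.

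| q | Expected of 30 | Chance of at least one |
|---|---|---|
| 2% | 0.6 | 0.46 |
| 5% | 1.5 | 0.79 |
| 10% | 3.0 | 0.96 |
| 20% | 6.0 | >0.99 |

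**4. What would the fix change?** Simulation with no drug effect: each participant has a true level drawn from a normal distribution (mean, between-person SD), and each visit adds independent normal noise (within-person SD). All means and SDs are assumed. The 12 post-baseline vital-sign visits follow from the 14 scheduled visits less screening and Day 1. The schedule of assessments shows two post-baseline ECGs, leaving aside early termination.

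B is the percentage outside at baseline, A the percentage ever outside after baseline, and C the percentage ever outside after baseline among those inside at baseline. The overlap, outside both before and after, is A − C × (1 − B).

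| Assumed mean / between SD / within SD | B | A | C | A − C | Overlap | Overlap, of 30 |
|---|---|---|---|---|---|---|
| Diastolic <60: 76/8/6 | 5.5 | 23.6 | 20.0 | 3.6 | 4.7 | 1.4 |
| Diastolic <60: 74/8/6 | 8.0 | 31.2 | 26.2 | 5.0 | 7.1 | 2.1 |
| Diastolic <60: 76/9/7 | 8.0 | 31.7 | 26.8 | 4.9 | 7.0 | 2.1 |
| Diastolic <60: 78/8/5 | 2.8 | 12.2 | 10.1 | 2.1 | 2.4 | 0.7 |
| Bazett QTc >450: 415/18/10 | 4.5 | 6.9 | 4.4 | 2.5 | 2.7 | 0.8 |

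Example, first row: 23.6 − 20.0 × 0.945 = 4.7%, and 30 × 0.047 = 1.4.

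If pre-dose values are counted as well, those outside only at baseline are added (B − overlap). For QTc this is 4.5 − 2.7 = 1.8, giving 6.9 + 1.8 = 8.7% against 4.4% for new onset. For diastolic pressure it adds 0.4 to 1.0 points.

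**The case against.** The strongest reply is that these are secondary descriptive displays with no decision rule, and that much of the information is available elsewhere. QTc increases above 30 and 60 msec are counted, the overall clinical ECG evaluation is summarized, and changes from baseline are given by sign and interval. SAP 4.1.2 puts all observations in listings, where each flagged person's baseline can be read. Clinically significant vital signs go through adverse event recording. SAP 4.1 leaves further presentation detail to a programming plan that is not among the documents. All of this stands, and it limits the point to a minor one. It does not remove it: which participants a table counts belongs in the SAP, and none of these outputs gives the split.

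A reader might go further in three directions that the documents do not support.

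- **Liver.** One might infer that the liver rows share the defect and could produce a false serious signal. They are already post-baseline, and the entry limits lie below every threshold. The exceptions are bilirubin raised above the limit "unless due to Gilbert's syndrome" and a rise between screening and Day 1. No frequency is given for either. Three of the four liver rows also carry a discontinuation criterion from Protocol 7.1.1 (8 × ULN; 5 × ULN for more than 2 weeks; the combined criterion), so conditioning them on baseline could hide a participant who met one. Nor would conditioning remove the scenario feared: a participant with Gilbert's syndrome and normal ALT does not meet the combined criterion at baseline and would still be counted after an ALT rise.
- **Diastolic crossing rates.** Column A might be read as the size of the defect. Most of it is within-person variation over 12 visits, which the fix leaves in place.
- **Posture.** Protocol 8.5.1 allows measurement "in a seated or supine position, after having sat calmly for at least 5 minutes". It does not say that position varies within a participant, and no effect can be estimated from the documents.

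**Conclusion.** The point holds for the vital-sign limits in SAP 4.8.3 and the three absolute QTc rows in SAP 4.8.5. As written, they put pre-existing and new values in one count, in a trial where baseline is the only comparator. The fever row is largely protected by exclusion 18; no other vital-sign or QTc limit has a numeric entry bound.

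On the assumed inputs, moving from any post-baseline crossing to new onset lowers the rate by about 2 to 5 points per limit, which on 30 people is 0.6 to 1.5. The participants who would move to the outside-at-baseline group number 0.7 to 2.1 of 30. If pre-dose values are also counted, the gap is somewhat wider. These sizes depend on means and SDs that no document supplies and on independent visit-to-visit noise. The wording gap does not depend on them.

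Severity is minor: a cheap clarification of two tables that does not affect the efficacy analysis or any formal decision.

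**What to change.** - In SAP 4.8.3 and the absolute QTc rows of SAP 4.8.5, count post-baseline values only.
- Show each row by baseline status, inside or outside the limit, with the number of participants in each group as its denominator.
- Retitle the vital-sign table 'outside predefined limits', leaving clinical significance to the investigator as Protocol 8.5.1 does.
- Leave the liver rows in SAP 4.8.2 unconditioned. At most, footnote any participant with Gilbert's syndrome in the rows that use bilirubin.

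The cost is a few words in the SAP and one extra column before database lock. The new-onset counts will be smaller and their denominators may fall below 30, but nobody is lost from view, because those outside at baseline remain in their own column.
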